6.19.1. Extent of Exposure

Duration of exposure to study drug will be summarized for the safety population by treatment group. Exposure will be calculated as the date of last dose of study drug (or date of discontinuation) minus the date of first dose of study drug plus 1 day. Total PYs of exposure will be reported for each treatment group for overall duration of exposure. Descriptive statistics (n, mean, SD, minimum, first quartile, median, third quartile, and maximum) will be provided for patient-days of exposure and the frequency of patients falling into different exposure ranges will be summarized. Exposure ranges are as follows:

- ≥ 4 weeks, ≥ 12 weeks, and ≥ 24 weeks
- >0 to <4 weeks, ≥ 4 weeks to <12 weeks, ≥ 12 weeks to <24 weeks, and ≥ 24 weeks

Overall exposure will be summarized in total PYs, which are calculated according to the following:

Exposure in PYs = sum of duration of exposure in days (for all patients in treatment group) / 365.25

No p-values will be reported in these tables as they are intended to describe the characteristics of the study sets.

6.19.2. Adverse Events

6.19.2.1. Adverse Events

AEs are recorded in the eCRF. Each AE will be coded to SOC and PT, using the MedDRA version that is current at the time of database lock. Severity of AEs is recorded as mild, moderate, or severe.

TEAEs are defined as events that either first occurred or worsened in severity after the first dose of study drug and the earliest of the visit study drug disposition date or the last visit date during the treatment period, whichever occurred first, and up to 30 days after study treatment discontinuation. The MedDRA LLT will be used in defining which events are treatment-emergent. The maximum severity for each LLT during the baseline period until the first dose of the study medication will be used as baseline. If an event is preexisting during the baseline period, but it has missing severity, and the event persists during the treatment period or up to 30 days after treatment discontinuation, then the baseline severity will be considered mild for

determining any postbaseline treatment-emergence (that is, the event is treatment-emergent unless the severity is coded mild at postbaseline). If an event occurring postbaseline has a missing severity rating, then the event is considered treatment-emergent. Should there be insufficient data for an AE start date to make this comparison (for example, the AE start year is the same as the treatment start year, but the AE start month and day are missing), the AE will be considered treatment-emergent. For events occurring on the day of the first dose of study treatment, the day and time of the onset of the event will both be used to distinguish between pretreatment and posttreatment in order to derive treatment-emergence.

In general, summaries will include the number of patients in the safety population (N), frequency of patients experiencing the event (n), and relative frequency (that is, percentage; $n/N*100$).

In an AE overview table, the number and percentage of patients in the safety analysis set who experienced death, an SAE, any TEAE, permanent discontinuation from study drug due to an AE, temporary interruption of study drug due to an AE or laboratory abnormality, or a severe TEAE will be summarized by treatment group.

The number and percentage of patients with TEAEs will be summarized by treatment group in 2 formats listed below. For events that are gender specific, the denominator and computation of the percentage will only include patients from the given gender.

- by MedDRA PT nested within SOC with SOCs ordered alphabetically, and events ordered within each SOC by decreasing frequency in the LY3471851 CCI treatment group.
- by MedDRA PT with events ordered by decreasing frequency in the LY3471851 CCI treatment group.

AEs leading to permanent discontinuation of study drug and AEs leading to temporary interruption of study drug will also be summarized by treatment group using MedDRA PT nested within SOC. Events will be ordered by decreasing frequency within SOC in the LY3471851 CCI treatment group.

CCI

CCI

The number and percentage of patients with TEAEs will be summarized by maximum severity by treatment using MedDRA PT ordered by decreasing frequency for the common TEAEs. For each patient and TEAE, the maximum severity for the MedDRA level being displayed is the

maximum postbaseline severity observed from all associated LLTs mapping to that MedDRA PT.

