9.4.5. Safety Analyses

Safety analyses will include AEs, SAEs, **CCI** C-SSRS, QIDS-SR16, vital signs, ECGs, and laboratory analytes, using the Safety Population data descriptively summarized by treatment group. Categorical safety measures will be summarized with incidence rates. Continuous safety

measures will be summarized as mean change by visit. Exposure to study intervention will be calculated for each participant and summarized by treatment group.

Adverse events will be coded according to the *Medical Dictionary for Regulatory Activities* (MedDRA) and summarized by system organ class, preferred term, severity, and relationship to the study intervention. A treatment-emergent adverse event (TEAE) is defined as an event that first occurred or worsened in severity after baseline, with baseline defined as all pre-existing conditions recorded at Visit 1 and any AEs recorded before the first dose of study intervention (that is, during the interval between Visits 1 and 2 and recorded with the time of onset before the first dose of study intervention). The treatment period will be used as the postbaseline period for the analysis. For events that are gender specific, the denominator and computation of the percentage will include only participants from the given gender.

The number and percentage of participants who experienced TEAEs, TEAEs by maximum severity, deaths, SAEs, TEAEs related to study intervention, discontinuations from the treatment due to an AE, CCI [REDACTED] will be summarized. Treatment-emergent adverse events (all, by maximum severity), SAEs including deaths, and AEs that lead to treatment discontinuation will be summarized and analyzed by MedDRA system organ class (SOC) and preferred term.

Treatment-related TEAEs (TEAEs related to study intervention) are defined as events that are indicated by the investigator on the eCRF to be related to treatment.

CCI [REDACTED]
[REDACTED]

Suicide-related thoughts and behaviors occurring during treatment will be summarized based on responses to the C-SSRS consistent with the C-SSRS Scoring and Data Analysis Guide (Columbia Lighthouse Project WWW).

Follow-up emergent AEs, SAEs including deaths, and AEs that lead to study discontinuation will be summarized. All AEs, including pre-existing conditions, will be listed by participant, visit, preferred term, treatment group, severity, and relationship to the treatment.

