10.1.9. Study and Site Start and Closure

The study start date is the date on which the clinical study is open for recruitment of participants.

The sponsor or designee reserves the right to close the study site or to terminate the study at any time for any reason at the sole discretion of the sponsor.

Closure of study sites

Study sites will be closed upon study completion. A study site is considered closed when all required documents and study supplies have been collected and a study-site closure visit has been performed.

The investigator may initiate study-site closure at any time, provided a reasonable cause exists and sufficient notice is given in advance of the intended termination.

Reasons for the early closure of a study site by the sponsor or investigator may include, but are not limited to, these:

- Failure of the investigator to comply with the protocol, the requirements of the IRB/IEC or local health authorities, the sponsor's procedures, or GCP guidelines
- Inadequate recruitment of participants by the investigator, and

- Discontinuation of further study intervention development.

Study stopping rules

The IAC will convene to evaluate unblinded safety data if

- 5 or more participants experience TEAEs in the same SOC or 3 or more participants experience a TEAE of CRS, and
- these TEAEs are judged as either serious or severe, and
- these TEAEs are related to blinded study treatment.

Study enrollment and/or further dosing may be stopped, pending the decision of the IAC (CCI [REDACTED] Section 10.1.5). If the study is not stopped, the IAC will meet periodically; details are provided in the IAC charter.

CCI [REDACTED]

If the study is prematurely terminated or suspended, the sponsor shall promptly inform the investigators, the IECs/IRBs, the regulatory authorities, and any contract research organizations used in the study of the reason for termination or suspension, as specified by the applicable regulatory requirements. The investigator shall promptly inform the participant and assure appropriate participant therapy and/or follow-up.

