6.19.2.2. Serious Adverse Events

An individual listing of all AEs including preexisting conditions will be provided. A separate listing will include AEs that led to permanent discontinuation from the study drug. In addition, a listing of AEs that occur more than 30 days after study treatment discontinuation will be provided.

With the ICH E2A guideline, a SAE is any AE that results in 1 of the following outcomes:

- death
- initial or prolonged inpatient hospitalization
- a life-threatening experience (that is, immediate risk of dying)
- persistent or significant disability/incapacity
- congenital anomaly/birth defect, or
- considered significant by the investigator for any other reason.

The number and percentage of patients who experienced any ICH-defined SAE will be summarized by treatment group during the treatment and follow-up periods using MedDRA PT nested within SOC. Events will be ordered by decreasing frequency within SOC in the LY3471851 CCI treatment group. In addition, the SAEs will be summarized by treatment group using MedDRA PT without SOC. An individual listing of all SAEs will be provided.

CCI [REDACTED]

[REDACTED]

[REDACTED]

[REDACTED]

[REDACTED]

[REDACTED]

[REDACTED]

[REDACTED]

CCI [Redacted]

[Redacted]

[Redacted]

[Redacted]

[Redacted]

[Redacted]

[Redacted]

CCI [Redacted]

[Redacted]

[Redacted]

CCI [Redacted]

[Redacted]

CCI [Redacted]

CCI [Redacted]

[Redacted]

[Redacted]

[Redacted]

[Redacted]

[Redacted]

CCI [Redacted]

[Redacted]

[Redacted]

[Redacted]

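### The SAP's one readable table of TEAE severity by term omits SOC and covers only common terms; the protocol sets neither limit

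*SAP*

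**What the plan says.** Protocol 9.4.5 groups three kinds of display: "Treatment-emergent adverse events (all, by maximum severity), SAEs including deaths, and AEs that lead to treatment discontinuation". It says that these "will be summarized and analyzed by MedDRA system organ class (SOC) and preferred term". An earlier sentence in the same section also names severity among the ways in which coded adverse events will be summarized. Neither sentence sets a frequency limit.

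SAP 6.19.2.1 gives all TEAEs in two formats. One is "by MedDRA PT nested within SOC with SOCs ordered alphabetically" and the other is by preferred term alone; neither is split by severity. For severity by term, the readable text has one table, in which TEAEs will be "summarized by maximum severity by treatment using MedDRA PT ordered by decreasing frequency for the common TEAEs". The sentence after it takes each participant's maximum over the lower-level terms that map to the preferred term, so the table stays at that level.

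Severity also appears in the overview table, whose contents end "temporary interruption of study drug due to an AE or laboratory abnormality, or a severe TEAE will be summarized by treatment group". SAP 6.19.2.2 adds a listing: "An individual listing of all AEs including preexisting conditions will be provided".

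**The concern.** The SAP narrows the protocol's display in two ways: the SOC level goes, and so do uncommon terms. Dropping SOC looks particular to this table, because the SAP's tables of all TEAEs, of SAEs, and of AEs leading to discontinuation or interruption all nest preferred terms within SOC.

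Protocol 9.4.1 says that a change of method which is not a principal feature will be described, with its justification, in the SAP and the study report. No justification for this change is readable.

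The trial is meant to guide dose selection and to describe benefit and risk (Protocol 2.1). If severe events at one dose fell under several related but individually uncommon terms, no readable by-arm table would show that they share an organ class. The SAE tables do not cover this, because Protocol 10.3.3 keeps severity and seriousness apart.

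**Working it through.** **1. The documents side by side**

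| By-arm display | Term level | Severity shown? | Limited to common terms? |
|---|---|---|---|
| Protocol 9.4.5, TEAEs by maximum severity | SOC and PT | yes | no |
| SAP 6.19.2.1, overview | none (one total per arm) | severe only | no |
| SAP 6.19.2.1, all TEAEs | PT within SOC; PT alone | no | no |
| SAP 6.19.2.1, AEs leading to discontinuation or interruption | PT within SOC | no | no |
| SAP 6.19.2.2, SAEs | PT within SOC; PT alone | no | no |
| SAP 6.19.2.1, maximum severity | PT alone | yes | yes |

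The parenthesis in Protocol 9.4.5 can be read as one display (all TEAEs, by maximum severity) or as two (all TEAEs, and TEAEs by maximum severity). Two is the more natural reading. Either way the severity display belongs under SOC and preferred term with no cut-off, so the comparison does not depend on the choice.

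A severe TEAE is missing from every by-arm table that identifies its type only if it is non-serious, did not lead to discontinuation or interruption, and belongs to an uncommon term. Even then the event is counted under its term in the all-TEAE tables, though not as severe, and it is in the overview total.

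**2. Illustration of how often a term would be left out**

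No figure in the documents is at stake, so there is none to reproduce. The only documented input is n = 70 per group (Protocol 9.2). As a check on it, take response rates 0.40 and 0.64 (SAP 6.1), with pooled rate 0.52:

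- SE under the null = √(2 × 0.52 × 0.48 / 70) = 0.0844
- SE under the alternative = √((0.40 × 0.60 + 0.64 × 0.36) / 70) = 0.0820
- z = (0.24 − 1.96 × 0.0844) / 0.0820 = 0.91, so power is about 82%, which agrees with the stated minimum of 80%.

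The cut-off t is an assumption, ranged from 1% to 10%. A term is shown if at least k = ceil(t × n) participants have it.

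| Assumed cut-off | One arm (n = 70): k; largest count omitted | Three active arms pooled (n = 210): k; largest count omitted |
|---|---|---|
| 1% | 1; 0 | 3; 2 |
| 2% | 2; 1 | 5; 4 |
| 5% | 4; 3 | 11; 10 |
| 10% | 7; 6 | 21; 20 |

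The chance that a term occurs in an arm yet falls below the cut-off is P(1 ≤ X ≤ k − 1), with X ~ Binomial(70, p). For p = 2%:

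- P(X = 0) = 0.98^70 = 0.243
- 2% cut-off: P(X ≤ 1) − P(X = 0) = 0.590 − 0.243 = 0.347
- 5% cut-off: P(X ≤ 3) − P(X = 0) = 0.948 − 0.243 = 0.705

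| True rate in the arm | 2% cut-off | 5% cut-off |
|---|---|---|
| 1% | 35% | 50% |
| 2% | 35% | 70% |
| 3% | 26% | 72% |

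Here p is the rate of the term at any severity, because common describes the term. A severe case of a common term would still be shown.

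**The case against.** The strongest reply is that little is lost. The AE listing covers every event, and Protocol 9.4.5 says that it carries preferred term, treatment group, severity and relationship, so type, severity and arm can be read together for any event. Severe TEAEs are totalled by arm. Serious and dose-affecting events are tabulated by SOC and term. Injection site reactions have their own maximum-severity summary (SAP 6.19.4), and hepatic and hematologic laboratory abnormalities have threshold or graded tables (SAP 6.19.5.1 and 6.19.5.2). This stands, and it sets the weight of the point. A participant-level listing is still not the by-arm summary that the protocol describes.

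The redaction argument also stands. Text just before the severity sentence is blacked out and may define common or hold another display. The missing definition is therefore no fault of the plan, and the absence of a justification can be stated only for the readable text.

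Three stronger readings are tempting, and the documents do not support them:

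- A reader might infer that rare severe events vanish from by-arm reporting. They do not; only their classification by term and SOC is lost, and only for the subset described above.
- A reader might link the table to the safety trigger in Protocol 10.1.9, which starts from "5 or more participants experience TEAEs in the same SOC or 3 or more participants experience a TEAE of CRS" and further requires that the events be serious or severe and be related. That trigger convenes the internal assessment committee during the study. Nothing says that it draws on this table, so the table's layout does not affect it.
- A reader might quote the chances of 59% and 95% that a term with a 2% rate misses the cut-off. Those include the 24% chance that the term never occurs in the arm, when there is nothing to lose.

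**Conclusion.** The difference between protocol and SAP is real on two counts: the severity table has no SOC level, and it is limited to common terms. The missing SOC level is the firmer part, because it does not depend on any cut-off.

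The loss is confined to the by-arm SOC and term classification of severe, non-serious TEAEs of uncommon terms that did not affect dosing, plus any SOC-level view of severity. How many terms are affected depends on an unreadable cut-off. Applied per arm, it ranges from none at an assumed 1% to terms seen in up to 3 participants at 5%, or 6 at 10%. The 35% and 70% figures rest on 70 per arm, a per-arm cut-off and a true rate of 2%.

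This is a reporting matter of minor weight. The primary analysis, the data collected and the Protocol 10.1.9 trigger are unaffected.

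**What to change.** In SAP 6.19.2.1, summarize all TEAEs by maximum severity and treatment group, by preferred term nested within SOC and also by preferred term alone. The table of common terms can stay as an extra.

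Alternatively, keep the common-term table as the main severity display, state the reason for the restriction as Protocol 9.4.1 asks, and add a by-arm table of severe TEAEs by SOC and preferred term.

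Either route costs one changed or added table shell. Severity and MedDRA coding are already recorded, so no new data are needed. The downside is a longer output.

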6.19.2.2. Serious Adverse Events

An individual listing of all AEs including preexisting conditions will be provided. A separate listing will include AEs that led to permanent discontinuation from the study drug. In addition, a listing of AEs that occur more than 30 days after study treatment discontinuation will be provided.

With the ICH E2A guideline, a SAE is any AE that results in 1 of the following outcomes:

- death
- initial or prolonged inpatient hospitalization
- a life-threatening experience (that is, immediate risk of dying)
- persistent or significant disability/incapacity
- congenital anomaly/birth defect, or
- considered significant by the investigator for any other reason.

The number and percentage of patients who experienced any ICH-defined SAE will be summarized by treatment group during the treatment and follow-up periods using MedDRA PT nested within SOC. Events will be ordered by decreasing frequency within SOC in the LY3471851 CCI treatment group. In addition, the SAEs will be summarized by treatment group using MedDRA PT without SOC. An individual listing of all SAEs will be provided.

CCI [REDACTED]

[REDACTED]

[REDACTED]

[REDACTED]

[REDACTED]

[REDACTED]

[REDACTED]

[REDACTED]

CCI [Redacted]

[Redacted]

[Redacted]

[Redacted]

[Redacted]

[Redacted]

[Redacted]

CCI [Redacted]

[Redacted]

[Redacted]

CCI [Redacted]

[Redacted]

CCI [Redacted]

CCI [Redacted]

[Redacted]

[Redacted]

[Redacted]

[Redacted]

[Redacted]

CCI [Redacted]

[Redacted]

[Redacted]

[Redacted]

6.19.3.3. Malignancies

Malignancies will be identified using terms from the Malignant tumors SMQ (SMQ 20000194). Malignancies excluding NMSC and NMSC will be reported separately.

A listing including all malignancy cases will be provided. An NMSC flag will be provided using the following MedDRA PTs (the list will be updated depending on the MedDRA version used for analysis):

- Squamous cell carcinoma of skin (10041834)
- Bowen's disease (10006059)
- Basal cell carcinoma (10004146)
- Basosquamous carcinoma (10004178)
- Basosquamous carcinoma of skin (10004179)
- Squamous cell carcinoma (10041823)
- Skin squamous cell carcinoma metastatic (10077314)
- Skin cancer (10040808), and
- Carcinoma in situ of skin (10007390).

The number and percentage of patients with TEAE-associated malignancies excluding NMSC and NMSC will be summarized by treatment group. In addition, the IR (for detail, see Section 6.19) and 95% CI will be calculated for the overall observation time. All cases identified by Malignant tumors SMQ will be assessed after database lock by the medical team to determine (1) confirmed NMSC cases and (2) symptom and date that triggered the malignancy investigation or diagnosis. An additional listing based on medical review may also be provided if deemed necessary. All cases reported in the study database or by Lilly Safety System report, disregarding the length of gap between the last treatment dose date and the event date will be included.

6.19.4. Injection Site Reaction

At every visit following the first dose and prior to any blinded study activity, an independent ISR assessor who is not involved with other study procedures will evaluate each participant for the presence of ISRs between the visits.

The number and percentage of patients who experienced an ISR will be summarized by treatment group and by visit. The number and percentage of patients with the following ISR records will be summarized by treatment group and by visit. Details about ISR records are referred to the case report form.

- anatomical location of the injection site reaction
- abdomen side
- directionality of the anatomical location of the administration
- arm side
- thigh side
- whether the subject have any injection site erythema (reddening) or not
- severity of the injection site erythema
- whether the subject have any injection site induration (hardening or thickening of tissue) or not
- severity of the injection site induration
- whether the subject have any injection site pain (including burning) or not

- severity of the injection site pain
- whether the subject have any injection site pruritus
- severity of the injection site pruritus
- whether the subject have any injection site edema (swelling or accumulation of fluid in tissues at height above normal skin) or not
- severity of the injection site edema, and
- when did the injection related event occur, in relationship to the study treatment.

The frequency of the maximum severity of ISRs will be summarized by treatment group.

CCI

It will not be considered a protocol violation if the planned sample size is not achieved due to an insufficient number of consenting and eligible participants.

6.19.5. Clinical Laboratory Evaluation

All laboratory tests will be presented using the Système International of units (SI) and conventional (CN) units. For topics of safety in special groups and circumstances, laboratory test units will be specified for each analysis.

Lilly LCTPB reference limits will be used to define the low and high limits because it is generally desirable for limits used for analyses to have greater specificity (identify fewer false positive cases) than reference limits used for individual patient management. When Lilly LCTPB reference ranges are unavailable, then central laboratory (Covance) reference ranges will be used. For the 4 key hepatic laboratory assessments (ALT, AST, total bilirubin, and ALP), central laboratory reference ranges (Covance) will be used and all results pertaining to these assessments will be included as a separate analysis to address the risk of liver injury as a special safety topic (see Section 6.19.5.1). Central laboratory reference ranges (Covance) will also be used to evaluate immunoglobulins and lymphocyte cell subsets (see Sections 6.19.5.3 and 6.19.5.7). See [Appendix 6](#) for details of the reference range by laboratory analytes.

The LDL/HDL ratio will be derived as the ratio of LDL cholesterol to HDL cholesterol. There are no Lilly LCTPB reference ranges or central lab reference ranges for the LDL/HDL ratio.

The following will be conducted for laboratory analyte measurements collected quantitatively:

- Box plots for observed values: Values at each visit (starting at randomization) and change from baseline to each visit and to last postbaseline measure will be displayed in box plots for patients who have a baseline and at least 1 postbaseline visit. For visits included in the treatment period, patients will be included only if the visit occurs on or before the date of treatment discontinuation/completion. Follow-up visit will be the first visit that occurred during the Follow-up period. Individual measurements outside of reference limits will also be displayed using distinct symbols overlaying the box plot. Original-scale data will be used for the display but for some analytes (for example, immunoglobulins) a logarithmic scale will be used to aid in viewing the measures of central tendency and dispersion. Unplanned measurements will be excluded. Descriptive summary statistics will be included in a table below the box plot. These box plots will be used to evaluate trends over time and to assess a potential impact of outliers on central tendency summaries. A p-value for change from baseline to endpoint will be provided using an ANCOVA model with explanatory term for treatment and the baseline value as a covariate. Endpoint will be the last observation where patient is on treatment.
- Treatment-emergent high/low analyses: the number and percentage of patients with treatment-emergent high and low laboratory results at any time will be summarized by treatment group. Planned and unplanned measurements will be included. A treatment-emergent **high** result is defined as a change from a value less than or equal to the high limit at all baseline visits to a value greater than the high limit at any time during the treatment period and up to 60 days after treatment discontinuation. A treatment-emergent **low** result is defined as a change from a value greater than or equal to the low limit at all baseline visits to a value less than the low limit at any time during the treatment period and up to 60 days after treatment discontinuation. The Fisher's exact test will be used for the treatment comparisons.

A listing of abnormal findings will be provided. The listing will include, but not be limited to, patient ID, treatment group, laboratory collection date, analyte name, and analyte finding.

